Concomitant meds ^k		----- Continuous -----									●			
Participant diary distribution ^l		●			●									
Participant diary review ^m			●			●								
Approx. blood draw per day, mL:	2	25		29.5	25		27.5		10		10			
Approx. cumulative blood draw, mL:	2	27		56.5	81.5		109		119					

●¹ pre vaccination; ●² pre and post vaccination; ●³ blood samples for immunogenicity will only be taken if the early exit visit is at least 10 days after the previous immunogenicity blood draw; ●⁴ if within 7 days of the previous vaccination; ●⁵ if within 28 days of the last vaccination; ●⁶ Screening diagnostic test for SARS CoV 2 past or current infection will be performed. Valid results taken within 28 days will also be acceptable; ●⁷ to be repeated pre vaccination if the screening test was done more than 4 days before Day 1

*The phone call or these visits (including their window) are to be scheduled relative to the actual day of the previous vaccination, indicated as Visit Timing days/weeks post Vac 2.

- Screening will be performed within 28 days prior to the first study vaccination or on the day of vaccination. If screening is performed on the day of vaccination, Visit 1 and Visit 2 will coincide on Day 1. Screening must be completed, and all eligibility criteria must be fulfilled prior to randomization and vaccination.
- If a participant shows COVID-19 like symptoms, the participant should contact the site for guidance and must follow their local country and site level recommendations for COVID-19.

- c. The site will contact the participant 7 days post vaccination 1, 7-days post vaccination 2, and 28 days post vaccination 2 to enquire about compliance of patient diary completion that occurred between the actual vaccination visit and the current day.
- d. Within 1 month, the site will contact any participants who have already had their 6-month post Vac 2 visit (Visit 6) but have not yet reached 12-months post Vac 2 for additional safety follow up.

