10.2. Appendix 2: Clinical Laboratory Tests

The following tests will be performed according to the Schedule of Activities (Section 1.4.1 and Section 1.4.2):

Laboratory Assessments	Parameters	Timepoints
Testing done locally/centrally	
 Urine pregnancy testing for participants of childbearing potential only Nasal swab sample and test for SARS-CoV-2 antibody Serology test for anti-SARS-CoV-2 N antibody Whole blood sample for platelet count which at some sites may be part of a complete blood count with differential Serum samples for humoral immunogenicity Serum/plasma samples for coagulation-related assays such as but not limited to: 
 Activated partial thromboplastin time Prothrombin time International normalized ratio Fibrinogen D-dimer Lupus anticoagulant Anti-cardiolipin antibody Beta-2 glycoprotein Heparin Induced Thrombocytopenia (HIT)/PF4 Ab, IgG·(HIT assay) Platelet activation assay (if HIT/PF4 is positive) Homocysteine ADAMTS13 Activity and Inhibitor Profile 	
 At screening and before each vaccination At screening and pre-vac 1 if the screening test was done more than 4 days before Day 1 At screening, At 28 days post-vac 1 and 14 days post-vac 2, and 24 weeks post-vac 2-. Testing may also be performed at 24 weeks post vac 2 from the humoral immunogenicity sample. Pre-vac 1, 28 days post-vac 1, pre-vac 2, and 14 days post-vac 2 with Ad26.COV2.S and as part of a (suspected) AESI investigation if applicable Pre-vac 1, 28 days post-vac 1, pre-vac 2, 14 days post-vac 2 and 24 weeks post-vac 2 Based on the clinical evaluation of the suspected AESI (eg, whether thrombocytopenia is observed with a thrombotic event), all or some of these tests may be conducted on the stored pre-vaccination sample (some of these tests will be conducted retrospectively) and on the samples obtained as part of the AESI investigation For all subjects from the main and sub study, at Pre-vac 1, 28 days post-vac 1, pre-vac 2, 14 days post-vac 2, all or some of these tests may be conducted on the samples (some of these tests will be conducted retrospectively)

Laboratory Assessments	Parameters	Timepoints

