5. STATISTICAL ANALYSES

5.1. General Considerations

5.1.1. Study Phases

A baseline (or reference) value will be defined as the value of the last available assessment prior to the first vaccination on Day 1, unless specified otherwise. The safety analysis will present all results by phase (see Section 5.2).

Immunogenicity results will be presented per scheduled time point as appropriate using visit windows (see section 1.4 in the protocol). Listings will be presented per phase and time point.

Study day or relative day is defined as follows:

Study Day = visit date - date of Day 1 + 1; if visit date \geq date of Day 1 (date of first vaccination).

Study Day = visit date - date of Day 1; if visit date $<$ date of Day 1 (date of first vaccination).

Relative day (relday), the number of days in the analysis time point will be defined as:

relday = visit date - reference date + 1 for visits on or after the reference date,

relday = visit date - reference date for visits before the reference,

where the reference date equals the date of vaccination 1 or 2.

The planned primary and final analysis will be performed on unblinded data. During primary analysis data will be unblinded to the sponsor.

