5.1.2. Phase Definitions

The phases in the study will be constructed, as follows in [Table 5](#)

Table 5: Phase Definitions

Phase	Phase #	Period	Period #	Interval	
				From	To
Screening	1			Date and time of signing the informed consent form	One minute prior to start of post dose 1 period
Post-dose	2	Post-dose 1	1	Date and time of first vaccination	Minimum of: a) 23:59 at the date of last contact (for early discontinuation) b) One minute prior to the date of unblinding visit or database cut-off date, whichever occurs first c) 23:59 on 28 days after the first vaccination (23:59 of day of vaccination + 28 days)
Follow-up 1	3			One minute after post-dose 1 period end	Minimum of: a) 23:59 at the date of last contact (for early discontinuation) b) One minute prior to the date of unblinding visit or database cut-off date, whichever occurs first c) One minute prior to date and time of second vaccination
Post-dose	2	Post-dose 2	2	Date and time of second vaccination	Minimum of: a) 23:59 at the date of last contact (for early discontinuation) b) One minute prior to the date of unblinding visit or database cut-off date, whichever occurs first c) 23:59 28 days after the second vaccination (23:59 of day of vaccination + 28 days)
Follow-up 2	4			One minute after post-dose 2 period end	Minimum of: a) 23:59 at the date of last contact (for early discontinuation) b) One minute prior to the date of unblinding visit or database cut-off date whichever occurs first

					c) One minute prior to 6 months after second vaccination
Follow-up 3	5			One minute after post-dose 2 period end	
Minimum of:
 
a) 23:59 at the date of last contact (for early discontinuation)
 
b) One minute prior to the date of unblinding visit or database cut-off date, whichever occurs first
 
c) 23:59 at the date of last visit

Note: the end of regimen phase should be the end of the last post dose period

FU3: Full follow-up from end of post dose 2 to end of study or last contact

Post-dose 1 and post dose 2 Combined includes events occurring in the post-dose 1 and/or post dose 2 phases (not including FU 1 or FU2 or FU3)

For final analysis the following criteria for Follow-Up 3 will be used 23:59 at date of last contact (for early discontinuation or date of last visit)

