5.3.4. Laboratory, Vital Signs and Physical Examination

Laboratory safety parameters, change from baseline and change from pre-dose over time will be tabulated. Abnormalities on the changes from reference, if available, may be categorized. Abnormalities may be tabulated by visit and by worst abnormality. Patient profiles may be provided.

A listing of all laboratory values will be made, restricted to participants with at least one laboratory abnormality.

Hematology laboratory parameters before and after Ad26.COV2.S administration.

Including but not limited to: Lupus anticoagulants, anti- β 2 glycoprotein, anti-cardiolipin, D-dimers, platelet count and anti-PF4

Physical examination findings will be summarized at baseline. A listing of the abnormalities will be made.

Vital signs including temperature, pulse/heart rate, respiratory rate, and blood pressure (systolic and diastolic) will be summarized over time, using descriptive statistics. Abnormalities emerging after vaccination will be tabulated by worst abnormality grade using the FDA table in [Appendix 2](#).

An abnormality (toxicity grade or abnormality based on normal ranges) will be considered as emerging in a particular period if it is worse than the baseline value. If the baseline is missing, the abnormality is always considered emerging. A shift from 'abnormally low' at baseline to 'abnormally high' post baseline (or vice versa) is also emerging. In case a laboratory test result is censored (no numeric value is available, but only a verbatim term) then a numeric value will be

imputed by a value exceeding the cut-off value with one unit. (<x: subtract 1 unit from x, >x: add 1 unit to x; <3.45 is imputed with 3.44).

In case no toxicity grades are defined for a test, the abnormalities (above/below normal range) will be used. In determining toxicity grades, the following rules are applied:

-worst grades/abnormalities are determined over the whole observational period for each trial period separately, including all post-baseline measurements of that period.

- The abnormalities 'abnormally low' and 'abnormally high' are considered equally important, i.e. if a participant has as well an abnormally low as an abnormally high value post-baseline, both abnormalities are shown in the tables. (This means that the sum of the percentages can be more than 100%)

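### In the Post-dose 2 period, SAP 5.3.4 judges emerging vital-sign and laboratory abnormalities against Day 1 only, so the flag does not show what changed after dose 2

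*SAP*

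**What the plan says.** SAP 5.3.4 states that an abnormality "will be considered as emerging in a particular period if it is worse than the baseline value". The periods are handled one by one: "worst grades/abnormalities are determined over the whole observational period for each trial period separately". Section 5.3.4 names no special reference for any period, so the general definition in SAP 5.1.1 applies, under which baseline is "defined as the value of the last available assessment prior to the first vaccination on Day 1, unless specified otherwise".

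The same section also plans this: "Laboratory safety parameters, change from baseline and change from pre-dose over time will be tabulated". It therefore treats baseline and pre-dose as two different quantities. The emerging rule uses only the first.

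SAP 5.1.2 (Table 5) ends Follow-up 1 at "One minute prior to date and time of second vaccination" and starts Post-dose 2 at the vaccination itself. The Day 57 pre-dose value thus belongs to Follow-up 1.

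The pre-dose 2 data are collected. Protocol 10.2 schedules platelet counts at "Pre-vac 1, 28 days post-vac 1, pre-vac 2, and 14 days post-vac 2 with Ad26.COV2.S". The Schedule of Activities (Protocol 1.4.1 and 1.4.2) marks vital signs at both vaccination visits as "pre and post vaccination".

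The tables differ in standing. SAP 5.3.4 commits to tabulating vital-sign abnormalities that emerge after vaccination, but only allows for laboratory abnormality tables.

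**The concern.** A column of abnormalities emerging in the Post-dose 2 period will be read as what appeared after the second dose. With a Day 1 reference it shows something else: what is worse than it was before any vaccine. Vital signs taken shortly after dose 2 are compared with readings 56 days old, although a reading from the same visit exists. Day 71 laboratory values are compared with values 70 days old.

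This can mislead in two ways. A finding that arose after dose 1 or between the doses, and was still there just before dose 2, is counted as emerging after dose 2. A finding that was present on Day 1, absent or milder at Day 57, and back after dose 2 at no worse than its Day 1 grade is left out.

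Elsewhere the SAP does separate the doses. Adverse events go to periods by start date and time (5.3.3.1), and immunogenicity results include a fold increase from pre-dose 2 (6.1.4). At stake is what the descriptive tables can say about the second dose.

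**Working it through.** The documents give no figure on this point, so there is none to reproduce. The check has two parts.

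**1. Logic of the rule.** Let d1, d57 and p be the toxicity grades (0 to 4) on Day 1, at Day 57 before dose 2, and at worst in Post-dose 2.

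- SAP rule: flag if p > 0 and p > d1.
- Pre-dose 2 rule: flag if p > 0 and p > d57.

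Of the 5 × 5 × 5 = 125 grade patterns:

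| Result | Patterns | Example (d1, d57, p) |
|---|---|---|
| Rules agree | 85 | 0, 0, 1 (both flag) |
| Flagged by the SAP, no worse than just before dose 2 | 20 | 0, 1, 1 |
| Worse than just before dose 2, not flagged by the SAP | 20 | 1, 0, 1 |

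The total is 85 + 20 + 20 = 125. These count patterns, not expected participants. All 20 unflagged patterns have an abnormal Day 1 grade. Such values can occur: a footnote to inclusion criterion 5.1 (Protocol 5.1) admits participants with Grade 1 or Grade 2 vital signs, and SAP Appendix 2 grades a respiratory rate of 17-20 as Grade 1.

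**2. Illustrative size with no vaccine effect.** None of these inputs is in the documents:

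- values at the three visits are trivariate normal with one common abnormality threshold;
- the proportion abnormal, q, is 5-20%;
- the correlation of Day 1 with each later visit, a, is 0.5-0.6 (the same for both visits);
- the correlation of Day 57 with the post-dose 2 value, b, is 0.6-0.8.

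Write A for P(abnormal on Day 1 and post-dose 2), B for P(abnormal at Day 57 and post-dose 2), and C for P(abnormal at all three).

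- Share of Post-dose 2 flags already abnormal before dose 2 = (B − C)/(q − A).
- Share of values newly abnormal since Day 57 that are not flagged = (A − C)/(q − B).

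Extremes over the grid:

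| q | a | b | A | B | C | Calculation | Result |
|---|---|---|---|---|---|---|---|
| 0.05 | 0.6 | 0.6 | 0.0155 | 0.0155 | 0.0077 | already present: 0.0078/0.0345 | 23% |
| 0.20 | 0.5 | 0.8 | 0.0872 | 0.1290 | 0.0645 | already present: 0.0645/0.1128 | 57% |
| 0.05 | 0.5 | 0.8 | 0.0122 | 0.0248 | 0.0077 | not flagged: 0.0045/0.0252 | 18% |
| 0.20 | 0.6 | 0.6 | 0.0992 | 0.0992 | 0.0638 | not flagged: 0.0354/0.1008 | 35% |

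**Sensitivity.** The SAP works with grades, and a rise from Grade 1 at Day 57 to Grade 3 after dose 2 is a real worsening that one threshold counts as already present. With four grades, each assumed one-third as frequent as the one below, the ranges become 17-44% and 14-27%.

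**The case against.** The strongest reply is that Day 1 is a legitimate convention. It is the only reference free of vaccine exposure. Under a pre-dose 2 reference alone, an abnormality caused by dose 1 that persists unchanged would drop out of the Post-dose 2 column. This stands, and is why Day 1 should be supplemented and not replaced.

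The likely impact is also limited. Safety is descriptive, with no formal testing (SAP 5.3). Graded laboratory and vital-sign shifts are not among the safety endpoints in SAP 5.3.1. The same rule applies to every dose group. The magnitude rests wholly on assumed inputs. All of this stands.

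Three stronger readings are tempting, and the documents do not support them:

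- **That the two doses cannot be separated at all.** Laboratory change from pre-dose is already planned, all laboratory values are listed for participants with any abnormality, vital signs are summarized over time, and adverse events are assigned by start time. The gap is in the emerging flag. It is widest for vital signs, for which 5.3.4 plans no change from pre-dose.
- **That TTS signals would be lost.** Platelet counts below 150,000/µL and thrombotic events are reported as suspected adverse events of special interest and adjudicated, whatever the baseline value (Protocol 8.3.6.1; SAP 5.3.2.1).
- **That new abnormalities are missed in general.** A miss needs a Day 1 value already abnormal at the same or a worse grade. After a normal or missing Day 1 value any Post-dose 2 abnormality is flagged, and so is a switch between abnormally low and abnormally high relative to Day 1.

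**Conclusion.** The point holds for the flag itself. Read together, SAP 5.1.1 and 5.3.4 leave Day 1 as the only reference in Post-dose 2, and the 0, 1, 1 and 1, 0, 1 patterns show both errors. They bear on the committed vital-sign table and on any laboratory abnormality table that is produced.

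The size is not known from the documents. Under the one-threshold assumptions, 23-57% of Post-dose 2 flags were already present before dose 2, and 18-35% of values newly abnormal since Day 57 are not flagged. A multi-grade rule gives different figures, and lower ones in the case tried.

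The consequence is confined to descriptive safety tables. Capture of TTS and other suspected events of special interest, the non-inferiority tests, alpha and power are unaffected. The change is worth making because it is cheap and lets the Post-dose 2 column be read as its title suggests.

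**What to change.** In SAP 5.3.4, add that for the Post-dose 2 period emerging abnormalities will also be derived and tabulated relative to the last value before the second vaccination (the Day 57 pre-dose value), beside the version referenced to Day 1. Keep Day 1 as the reference for Post-dose 1 and Follow-up 1, and label each column with its reference.

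The cost is one extra reference variable in the laboratory and vital-sign datasets and one extra column in the affected tables. No new data are needed, and keeping the Day 1 version means that persistent effects of dose 1 stay visible.

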5.4. Immunogenicity

5.4.1. General Considerations

Immunogenicity results will be presented by vaccine group and per scheduled time point as appropriate using visit windows (see Section 5.1.3).

For the PPI analysis samples taken outside of the allowed window as described in section 5.1.3 will be excluded from the table and graphs (but will be included in the listing and clearly marked as results not included in the PPI analyses). For the FAS analysis, samples taken outside of the allowed windows will be included in the tables and graphs.

Listings will be presented by vaccine group and per phase and analysis time point.

Key immunogenicity subgroup analyses will also be performed by BMI, ethnicity, race, sex, participants who were infected with SARS-CoV-2 during the study or those that received an alternative vaccine. Categorical variables will be summarized with a frequency table showing counts and percentages. This will be done for both the main study and sub study separately. Continuous variables will be summarized using the following statistics, as appropriate:

number of observations, geometric mean, arithmetic mean (mean), 95% confidence interval (CI) for the mean, standard deviation (SD), standard error (SE), median, quartiles (Q1 and Q3), minimum and maximum. This will be done for both main study and sub study separately.

Data listings, subject profiles and/or subject narratives may be provided as appropriate. This will be done for both main study and sub study separately.

Binary variables will be summarized using the following statistics: number of observations, percentages and Exact Clopper-Pearson 95% confidence interval (CI). This will be done for both main study and sub study separately.

